9.6.2. Method of Detecting AEs, AESIs and SAEs

Care will be taken not to introduce bias when detecting AEs and/or AESIs and/or SAEs. Open-ended and non-leading verbal questioning of the participant is the preferred method to inquire about AE occurrence.

9.6.3. Follow-up of AE, AESI and SAE

After the initial AE/AESI/SAE report, the Investigator is required to proactively follow each participant at subsequent visits/contacts. All SAEs, and non-serious AESIs (as defined in [Appendix 2: Adverse event and serious adverse event definitions](#)) will be followed until resolution, stabilization, until the event is otherwise explained, or the participant is lost to follow-up. Further information on follow-up procedures is given in [Appendix 2](#).

9.6.4. Regulatory Reporting of Serious Adverse Events

Procedure for SAE declaration by Investigator to Sponsor:

The Sponsor's PV contact for the study is:

BIOTRIAL

Email: [contact]

The Principal Investigator (PI), or designee, is responsible for providing notification to the Sponsor's PV contact of any SAE, whether deemed IMP-related or not, that a participant experiences during his participation in the study within 24 hours of becoming aware of the event. For all SAE Report Forms faxed or emailed, the PI must sign and date the form.

In addition, within one business day of receipt by Sponsor's PV contact any other requests for clarification of reported SAE data, and as appropriate, a list of any source documentation to be requested from the site (e.g. admission/discharge summaries, relevant to the events reported, lab/radiology/procedure reports, death certificate, autopsy report, etc.) are sent to the Sponsor.

Follow up information must be reported to the Sponsor's PV contact and within 24 hours of the study site staff becoming aware of new information.

The Sponsor's PV contact will be responsible for reporting all expedited reports like SAEs, expected SADR and SUSARs occurring in this study to competent authorities, FAMHP (Federal Agency for Medicines and Health Products), Ethics Committee and European Medicines Agency (EMA) according to applicable guidelines.

If an AESI occurs, the PI (or designee) will not be required to fill out a form, but must record the AE in the eCRF. The Sponsor will assess the AEs on a case-by-case basis to determine whether an AE is considered an AESI and, if necessary, will request that the PI (or designee) fill out a PV report form to document the event. The BIOTRIAL PV contact will then perform any further actions that may be required.

9.6.5. Treatment of Overdose

There is no known antidote in case of excessive dosing (beyond that prescribed in the protocol and including overdose). A symptomatic/supportive treatment will be provided.

Excessive dosing will be recorded in the eCRF. Any SAE or AE associated with excessive dosing must be followed as any other SAE or AE. These events are only considered AEs or SAEs if there are associated clinical signs and symptoms or if the act of taking the excess medicine itself is an AE or SAE.

9.7. Safety Assessment

9.7.1. Physical Examination

The timing of the complete physical examinations is provided in [Section 2](#), SoA.

The physical examinations will be performed by the Investigator or his representatives. A complete physical examination will include, at a minimum, assessments of the cardiovascular, respiratory, gastrointestinal, dermatological, neurological (including basic neurological testing for isocoria, light reflexes, gait and balance), musculoskeletal and lymphatic systems, in addition to head, eyes, ears, nose, throat, and neck. The physical examination will not include rectal examinations.

Further examination of other body systems may be performed in case of evocative symptoms at the Investigator's discretion.

Any abnormality identified at baseline should be recorded as medical history.

At subsequent visits (or as clinically indicated), limited, symptom-directed physical examinations should be performed (abbreviated physical examination). Changes from baseline abnormalities should be recorded in participant's notes. New or worsened clinically significant abnormalities should be recorded as adverse events on the eCRF.

9.7.2. Weight, height and BMI

The timing of the body weight and height measurements is provided in [Section 2](#), SoA.

Height will only be measured at screening, and used for calculating BMI at that visit.

9.7.3. Vital Signs

9.7.3.1. Parameters

Measured parameters: Supine systolic blood pressure (SBP), diastolic blood pressure (DBP) and heart rate (HR), body temperature.

9.7.3.2. Method of assessment

Qualified staff members will perform blood pressure (BP) measurements. If possible, BP measurements will be taken from the arm used for the infusion (opposite of the arm that is used for blood sample collection) by an automated BP monitor using the oscillometric method (e.g., Dinamap®). If there is a clinically important change in BP from the previous recording, measurements will be repeated immediately to confirm the change.

BP and HR will be measured using an automatic device for each participant, after at least 5 minutes at rest in the supine position.

The timing of the assessments is summarised in [Section 2](#), SoA.

The following normal ranges will apply:

Table 9: normal ranges for vital signs

Systolic blood pressure (mmHg)	Diastolic blood pressure (mmHg)	Heart rate (bpm)	Tympanic temperature (°C)
$90 \leq \text{SBP} \leq 150$	$50 \leq \text{DBP} \leq 90$	$40 \leq \text{HR} \leq 100$	$36.0 \leq t^{\circ} \leq 37.5$

9.7.4. Telemetry monitoring

9.7.4.1. Parameters

SpO₂, non-artifact events [arrhythmias, bradycardia, tachycardia, pause, ventricular tachycardia (VT), supraventricular tachycardia (SVT)].

9.7.4.2. Method of assessment

A centralised, continuous and automatic evaluation of the ECG signal is carried out. The telemetry traces will be monitored in real time. Alerts are triggered as soon as an abnormal event occurs. Alerts are reviewed by the investigator and considered for safety management of the participants. In the treatment period, cardiac telemetry monitoring will begin 1 hour prior to study drug administration and continue until 12 hours postdose.

9.7.5. Standard 12-lead ECG

9.7.5.1. Parameters

- Measured parameters: HR, PR interval, QRS duration, QRS axis, QT interval;
- Derived parameters: two corrections of the QT interval will be investigated: Fridericia's correction (QTcF) and Bazett's correction (QTcB).
- Observations and comments on the quality of the trace (if needed), on normality or abnormality.

9.7.5.2. Method of assessment

The timing of the assessments is summarised in [Section 2](#), SoA.

The measurements will consist of 12-lead digital ECGs. Participants must rest in the supine position for at least 5 minutes before the ECG recording is started. The ECG may be recorded during the period of rest required before the measurements of supine blood pressure and pulse. A qualified physician will review the ECGs promptly and any clinically important finding will be recorded on the appropriate CRF. The Investigator is responsible for providing the interpretation of all ECGs.

Table 10: normal ranges for ECG parameters

PR (ms)	QRS (ms)	QT_{cF}(ms)	Heart rate(bpm)
110 ≤ PR ≤ 220	QRS ≤ 120	QT _c ≤ 450 ms	40 ≤ HR ≤ 100

9.7.6. Laboratory safety parameters

9.7.6.1. Serology, drug screen and alcohol breath test

Blood tests will be carried out to test for the presence of HIV antibodies, hepatitis B surface antigen (HBsAg), and hepatitis C virus (HCV) antibodies.

Urinary screening will be carried out to test for amphetamines, benzodiazepine, cocaine, opiates, barbiturate and cannabinoids.

An alcohol breath test will be performed.

The timing of the assessments is summarised in [Section 2](#), SoA.

9.7.6.2. Laboratory Safety

9.7.6.2.1. Blood safety analysis

The following parameters will be determined:

- **Haematology:**
 - Haematocrit, haemoglobin, red blood cell count, WBC count, WBC differential count, platelets counts.
- **Safety coagulation:**
 - activated Partial Thromboplastin Time (aPTT).
- **Blood chemistry:**
 - fasting glucose, creatinine, urea, sodium, potassium, calcium, chloride, phosphorus, bicarbonate.
 - AST, ALT, GGT, alkaline phosphatase.
 - total bilirubin (fraction of direct bilirubin in case > 1.25 x ULN).
 - albumin, total protein.
 - LDH, CK (and fraction of CK-MB if > 1.5 x ULN).

NB: The baseline chemistry sample (predose sample) will also contain an extra archive serum sample for anti-Borrelia serology testing as backup to test for anti-Borrelia antibodies suggestive of previous exposure to **tick bites** in case of outlying results for PK/PD.

9.7.6.2.2. *Urinalysis parameters*

The following parameters will be investigated by microscopic examination of the sediment: cylinders, erythrocytes, leucocytes.

9.7.6.2.3. *Method of assessment*

Samples of blood will be collected in fasted conditions at the visits summarised in [Section 2](#), SoA.

For all clinically significant abnormal laboratory test values identified after investigational product administration, testing will be repeated until the values return to normal or baseline. If laboratory values do not return to normal or baseline within a reasonable period, the aetiology should be identified and the Sponsor notified.

Samples of urine will be collected at the visits summarised in [Section 2](#), SoA.

9.7.6.2.4. *Laboratory safety determinations*

Laboratory tests will be performed by Clinical Biology Department of CHU of Liège, [name], Belgium.

All clinical laboratory analyses will be performed at the local laboratory. Alcohol test, urine drug screen, will be performed at the clinical site by study personnel.

Serology (HIV and Hepatitis B and C testing) will be performed only at the Screening Visit;

Urine drug screen and alcohol breath test will be performed at the Screening Visit and D-1.

9.7.7. Occult Blood in Faeces

9.7.7.1. Parameters

Absence/presence of occult blood in faeces.

9.7.7.2. Method of assessment

Faeces samples will be collected at the timepoints listed in the SOA, section 2, Hemocult® testing will be performed to investigate any presence of occult blood in faeces.

Positive findings will be recorded as AEs, and also analysed as AESIs.

9.7.8. Tick bite exposure monitoring

9.7.8.1. Parameters

Absence/presence of exposure to tick bites.

9.7.8.2. Method of assessment

As highlighted in [Section 9.7.6.2.1](#), an extra sample for serology testing as backup to test for anti-Borrelia antibodies (IgG and IgM) suggestive of previous exposure to **tick bites** is drawn at baseline.

At the extra-ambulatory visits and samplings performed for ADA analysis, the participants will be asked if they have been exposed to tick bite since the previous visit (response recorded as yes/no/unknown). If the answer is yes, then the participant will be asked to

provide information on treatment (e.g. antibiotics) and on presence of *erythema migrans* and other signs or symptoms.

10. DATA MANAGEMENT AND STATISTICS

10.1. Data entry and management

10.1.1. Data collection

Electronic Data Capture (EDC) via eCRFs will be used for this study. For each participant who was exposed to study drug, an eCRF must be completed and signed electronically by the investigator or co-investigator. This also applies to those participants who fail to complete the study. If a participant withdraws from the study, the reason must be noted on the eCRF. eCRFs are to be completed on an ongoing basis.

Study data will be collected by the investigator or dedicated study personnel. Data will be collected on source documents and entered by the study personnel into the eCRFs in a timely manner.

All the documents must be archived for a minimum of 25 years or according to the Sponsor's procedures, whichever is longer.

Supplemental ADA samplings ("long-term follow-up of ADAs"):

ADA analysis data (including tick bite information if applicable) collected at the additional samplings after D180 will be collected in source documents and not in the eCRF. The results will be forwarded to the Sponsor after each time-point, and at the end of the follow-up period, individual ADA data will be forwarded to Biotrial.

10.1.2. Data coding

Biotrial will ensure coding for adverse events, prior and concomitants medications and medical history up to D180 in compliance with the Medical Dictionary for regulatory activities (MedDRA) and the World Health Organization Drug Dictionary (WHODDRUG), using the most recent versions of MedDRA and WHODDRUG.

10.1.3. Data validation

Biotrial will prepare the data validation document.

For each part, Biotrial will organise a Blind Review of the data before database locking.

Supplemental ADA samplings ("long-term follow-up of ADAs"):

The data lock-point date will be the D180 visit and the database will not be unlocked to add ADA data after this date. All data are unblinded from that point onwards. No influence of breaking the blind is anticipated on the dynamics of ADA.

10.2. Statistical considerations

10.2.1. Sample size

The number of participants is not based on statistical power considerations. A sample size of 8 participants per panel (i.e., 6 active and 2 placebo) was chosen based on the design of similar SAD studies and is considered adequate to provide an initial assessment of the safety and tolerability profile.

10.2.2. Statistical methods

The statistical analyses will be performed by the Biostatistics Unit of Biotrial Biometrics using SAS® software version 9.4 or higher release (SAS Institute Inc., Cary, NC, USA).

Pharmacokinetic data will be analyzed by Biotrial using Phoenix® WinNonlin® version 8.1 or higher (Certara USA, Inc., Princeton, NJ) and SAS® software Version 9.4 or higher release (SAS Institute Inc., Cary, NC, USA).

Descriptive statistics will be supplied according to the nature of the criteria:

- Quantitative variable: sample size, arithmetic mean, standard deviation (SD), standard error of the mean (SEM), minimum, median and maximum, and quartiles if necessary (with geometric mean, arithmetic and geometric coefficients of variation (CV), and quartiles for PK parameters).
- Qualitative variable: sample size, absolute and relative frequencies per class

The statistical analysis will be performed separately for each part of the study.

In each part of the study, all listings will be presented by treatment group and participant.

All listings will be presented by treatment group and participant.

No interim analysis is planned.

Further details on statistical analysis will be described in the Statistical Analysis Plan, agreed by the Sponsor.

10.2.3. Description of data sets

10.2.3.1. Definition of data sets

In each part of the study, the following data sets will be defined:

The Included set will be defined as all included participants who have signed an ICF.

The Randomised set will be defined as all randomised participants.

The Safety set will be defined as all included participants who have received at least a partial dose of IMP (Ir-CPI or placebo).

The Pharmacodynamic set will be defined as all the included participants who have completed the study without any protocol deviation affecting PD evaluation and with at least one available post-baseline PD data.

The Pharmacokinetic set will be defined as all the included participants who have been administered a complete infusion of IMP without major protocol deviation affecting PK evaluation. The inclusion of the subjects with incomplete PK profile(s) or incomplete infusion will be discussed before the PK concentration dataset is locked.

The analysis sets will be validated during the blind-review meeting.

10.2.3.2. Description of the sets

A summary table with the description of the number of included participants, the number of randomised participants, the number of participants who completed the study, the number of participants who discontinued classified by reason of withdrawal, the number of participants in each analysis set will be performed by treatment group and overall. Corresponding individual listings will be prepared.

Listings with analysis sets, end of study status and visit dates will also be carried out. A specific listing with discontinued participants will be also prepared as well as a listing of participants excluded from analysis sets.

10.2.4. Demographic and baseline characteristics

The following analysis will be performed on the Randomised set.

The participants' demographic characteristics and baseline characteristics will be summarised by treatment group and overall and listed.

Tables by treatment group and overall with the number of participants having at least one medical or surgical history and a corresponding listing will be prepared.

Tables by treatment group and overall with number of participants having at least one previous treatment will be prepared. The same table will be prepared for concomitant treatments.

Details of drug dosing and meals will be listed.

10.2.5. Protocol deviations

A summary table by treatment group and overall of protocol deviations and the corresponding listing will be prepared.

10.2.6. Pharmacokinetic analysis

The analysis will be performed on the Pharmacokinetic Set.

Relevant PK parameters will be calculated for Ir-CPI by non-compartmental or compartmental methods, as appropriate for those participants with sufficient plasma and urine concentration data (as described in Section 9.3).

10.2.6.1. Plasma concentration and PK parameters

Plasma concentrations of Ir-CPI will be summarised over time by treatment group and corresponding listings will be prepared.

Time profile plots will be prepared on linear and log-linear coordinates for each participant, as well as arithmetic mean (\pm SEM) by treatment group.

PK parameters will be summarised by treatment group and corresponding listings will be prepared.

Scatter plots and/or box whisker plots will be generated for the comparison of C_{\max} , AUC_{0-6} and AUC_{inf} .

For each part, the linear dose-proportionality of C_{\max} , AUC_{0-6} and AUC_{inf} (if applicable) will be assessed for parent (and metabolites if appropriate) using an exponential regression model ("power model"). The log-transformed PK parameter will be compared among the dose groups by using a 1-factor analysis of variance (ANOVA), with log-transformed dose as a fixed effect and participant as random effect.

10.2.7. Pharmacodynamic analysis

10.2.7.1. Criteria

- PD aPTT

- Factor XI and Factor XII inhibition

10.2.7.2. Statistical methodology

Analysis of pharmacodynamic parameters will be performed on the Pharmacodynamic set. For each parameter, descriptive statistics will be provided by treatment group on values and changes from baseline for each timepoint.

All pharmacodynamic parameters will be listed.

10.2.8. Exploratory Pharmacokinetic / Pharmacodynamic analysis

As an exploratory analysis, evaluation of the relationship between doses and concentrations of Ir-CPI and the change from baseline in coagulation parameters defined above will be graphically investigated and displayed.

10.2.9. Exploratory biomarkers' analysis

10.2.9.1. Criteria

- Serum cystatin C (CysC),
- TNF α ,
- hsCRP,
- D-dimers,
- Fibrinogen,
- PT,
- ADA,
- Urinary microalbumin, Kidney Injury Molecule (KIM-1), urinary neutrophil gelatinase-associated lipocalin (NGAL).

10.2.9.2. Statistical methodology

Analysis of exploratory parameters will be performed on the Pharmacodynamic set.

For each parameter, descriptive statistics will be provided by treatment group on values and changes from baseline for each timepoint. Graphs over time by treatment group will be also produced.

Presence of ADAs will be described by treatment group and timepoint until D180.

All exploratory parameters will be listed.

Supplemental ADA samplings ("long-term follow-up of ADAs"):

Results after D180 will be listed when applicable and the listing will be appended to the final CSR.

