9.2.2. Plasma pharmacokinetic analysis

The plasma pharmacokinetic analysis will be performed on the PKS set.

Subjects receiving placebo will not be included in the summary and analysis of PK parameters. Listings with plasma concentrations (including dates and times of PK blood sampling) and PK parameters will be provided by treatment group and subject. These listings will be generated for all subjects with an available PK profile (complete or incomplete), including those who are excluded from the PKS.

Plasma concentrations and PK parameters of Ir-CPI including descriptive statistics will be presented in tables separately for each treatment group.

Individual plasma concentration versus time profiles of Ir-CPI will be presented graphically on linear and log/linear coordinates for each subject.

The graph of arithmetic mean \pm SEM over time will be provided for plasma concentration of Ir-CPI on linear and log/linear coordinates with all treatment groups (cohorts A, B, C and D) on the same graph. A reference line corresponding to the lowest C_{max} values at the NOAEL (No Observed Adverse Effect Level), i.e. 53.7 μ g/mL will be added on the graph of mean and individual concentration-time profiles on log/linear coordinated only.

A graph of arithmetic mean \pm SEM with min-max curves over time will be provided for plasma concentration of Ir-CPI for each treatment group on linear coordinates.

Individual plasma concentration-time profiles (spaghetti plots) of Ir-CPI will also be presented for each treatment group on linear coordinates.

Box whisker plots will be generated for the comparison of C_{max} , AUC_{0-6h} , AUC_{0-96h} , AUC_{0-last} and AUC_{0-inf} .

The linear dose-proportionality of the maximum concentration (C_{max}) and the areas under the concentration-time curve (AUC_{0-6h} , AUC_{0-96h} , AUC_{0-last} and AUC_{0-inf}) will be assessed for Ir-CPI using an exponential regression model ("power model") that measures the degree of non-linear proportionality [2]. The PK parameter and dose values will be logarithmically

transformed prior to analysis and evaluated using a 1-factor analysis of variance (ANOVA) including log (dose) as fixed effect and subject as random effect.

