16.2.4	Demographic data and baseline characteristics
16.2.4.1	Demographic data – Randomised set
16.2.4.2	Other baseline characteristics
16.2.4.2.1	Subjects' habits – Randomised set
16.2.4.2.2	Serology – Randomised set
16.2.4.2.3	Urine drug screen – Randomised set
16.2.4.2.4	Alcohol breath test – Randomised set
16.2.4.2.5	Birth control method – Randomised set
16.2.4.3	Medical and surgical history and procedures
16.2.4.3.1	Medical history – Randomised set
16.2.4.3.2	Surgical history – Randomised set
16.2.4.3.3	Concomitant procedures – Randomised set
16.2.4.4	Previous and concomitant medications
16.2.4.4.1	Previous medications – Randomised set
16.2.4.4.2	Concomitant medications – Randomised set

NUMBER	TITLE
16.2.5	Compliance and/or drug concentration data
16.2.5.1	Compliance and dosing data
16.2.5.1.1	IMP administration – Randomised set
16.2.5.1.2	Meals intake – Randomised set
16.2.5.2	Pharmacokinetic data
16.2.5.2.1	Plasma concentrations and pharmacokinetic parameters
16.2.5.2.1.1	Plasma concentrations – Randomised set
16.2.5.2.1.2	Individual plasma concentration-time curves – Pharmacokinetic set
16.2.5.2.1.3	PK parameters in plasma – Randomised set
16.2.6	Pharmacodynamics data
16.2.6.1	Pharmacodynamic parameters – Pharmacodynamic set
16.2.6.2	Exploratory biomarker parameters – Pharmacodynamic set
16.2.7	Adverse event listings
16.2.7.1	Treatment-emergent adverse events – Randomised set
16.2.7.2	Adverse events for special interest – Randomised set
16.2.7.3	All adverse events – Randomised set
16.2.8	Clinical laboratory data
16.2.8.1	Haematology
16.2.8.1.1	Normal ranges for SI units and local units
16.2.8.1.2	PCSA ranges
16.2.8.1.3	All haematology values (SI unit) – Randomised set
16.2.8.2	Blood chemistry
16.2.8.2.1	Normal ranges for SI units and local units
16.2.8.2.2	PCSA ranges
16.2.8.2.3	All blood chemistry values (SI unit) – Randomised set
16.2.8.3	Coagulation
16.2.8.3.1	Normal ranges for SI units and local units
16.2.8.3.2	PCSA ranges
16.2.8.3.3	All coagulation values (SI unit) – Randomised set
16.2.8.4	Urinalysis – Randomised set
16.2.9	Other safety parameters
16.2.9.1	Vital signs data – Randomised set
16.2.9.2	Electrocardiogram data - Standard 12-lead ECG parameters – Randomised set

NUMBER	TITLE
16.2.9.3	Physical examination – Randomised set
16.2.9.4	Telemetry monitoring – Randomised set
16.2.9.5	Occult blood in faeces – Randomised set
16.2.9.6	Exposure to tick bites– Randomised set

BIOTRIAL

DRUG EVALUATION AND PHARMACOLOGY RESEARCH

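### SAP Appendix 4 confines the biomarker tables, graphs and listing to the Pharmacodynamic set, so an excluded participant's renal-injury and inflammatory markers appear in no planned output

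*Protocol*

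**What the plan says.** Protocol 10.2.7.2 and 10.2.9.2 end with parallel promises: "All pharmacodynamic parameters will be listed" and "All exploratory parameters will be listed". Each section first names its analysis set; for the biomarkers, "Analysis of exploratory parameters will be performed on the Pharmacodynamic set". SAP section 12 repeats both the set and the listing promise.

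The set itself (protocol 10.2.3.1, SAP 7.1) requires that the participant completed the study, "without any protocol deviation affecting PD evaluation", and has at least one post-baseline PD value. The PK set has a narrower deviation test: only a major deviation excludes.

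The population labels are in SAP 16.4 (Appendix 4):
- listing 16.2.6.1: "Pharmacodynamic parameters – Pharmacodynamic set"
- listing 16.2.6.2: "Exploratory biomarker parameters – Pharmacodynamic set"
- biomarker table 14.2.3.2.1 and graphs 14.2.3.2.2: also the PDS.

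For PK, SAP 9.2.2 takes the opposite course. Concentrations and parameters are listed for every participant with a PK profile, "including those who are excluded from the PKS".

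**The concern.** The exclusion rule is built around coagulation. Protocol 9.4.1 defines the PD outcomes as PD aPTT and residual FXI and FXII activity. A problem with those assays need not say anything about the validity of KIM-1, NGAL, urinary microalbumin or cystatin C. Yet it takes them out of the summaries and the individual listing together.

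Safety is the primary objective of this first-in-human trial. In the pivotal 24-hour monkey study (protocol 3.1 and 3.2) the adverse microscopic finding was in the kidney. It occurred at the super-high dose only, and a direct drug effect was suggested. The renal-injury markers are the trial's more specific look at that organ. With six active participants per dose, a signal in one person is mostly seen in the listings, so a listing that omits an excluded participant loses what it is most useful for.

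**Working it through.** The plan gives no figure to reproduce. The check traces where each marker can appear and then counts what is at stake.

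**1. Set labels of the subject listings (SAP 16.4, section 16.2), counted by hand**
- Randomised set: 31
- Included set: 4
- Screened set: 1
- Pharmacokinetic set: 1 (individual concentration curves)
- Pharmacodynamic set: 2

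Total: 31 + 4 + 1 + 1 + 2 = 39 listings that name a set. The two PDS listings are exactly the PD and the exploratory biomarker listings.

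**2. Other outputs that could carry the markers**
- Safety laboratory data (protocol 9.7.6.2, SAP 13.2): the renal chemistry is creatinine and urea, and the urinalysis is cylinders, erythrocytes and leucocytes. None of the six markers is included.
- First SAP appendix (13AUG2020): compartmental PK, PK/PD and ADA. It plans to list all ADA data, so ADA may be recovered there. The six markers are not covered.
- Second SAP appendix (12NOV2020): PK parameters and aPTT ratio by ADA group. The six markers are not covered.

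No planned output on a wider set carries them.

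**3. Scheduled values per participant (SAP section 12)**
- hsCRP: predose, 2, 4, 6, 8, 12, 24, 48 and 72 h, discharge = 10
- TNF-alpha: same times = 10
- Cystatin C: screening, predose, 24 h, 72 h, discharge = 5
- Urine: 4 collections × 3 markers = 12

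Total: 10 + 10 + 5 + 12 = 37. Renal: 5 + 12 = 17. Renal after the start of infusion: 3 cystatin C + 3 collections × 3 markers = 12.

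The schedule grids in SAP 16.1 also tick cystatin C on D3, which the footnotes and section 12 do not. Counting that tick gives 38 in total and 18 renal. A participant who withdraws early would have fewer.

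**4. Share of a group per exclusion**
- Active dose group: 1/6 = 16.7%
- Pooled placebo, 4 cohorts × 2 = 8: 1/8 = 12.5%

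On the Randomised set the listings would cover all 4 × 8 = 32 planned participants (24 active, 8 placebo) with available data.

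**The case against.** **The SAP follows the protocol.** A reader might infer that the SAP breaks a protocol promise to list everyone. The documents do not support that. The protocol itself puts both analyses on the PDS, and its listing sentences speak of all parameters, not all participants. The Appendix 4 labels can be read as carrying that set through, so there was no clear change to declare in SAP section 5. This objection stands. What remains is an inconsistency between how PK and PD or biomarker listings treat excluded participants.

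**A renal problem would still be visible.** A reader might infer that no renal or inflammatory signal in an excluded man could appear in the report. That goes too far. Creatinine, urea and urine sediment are analysed on the Safety set and listed on the Randomised set. Clinically relevant laboratory abnormalities are adverse events, also listed on the Randomised set. Excluded participants are themselves listed with reasons. What is lost is the specific markers.

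**PD evaluation may be wider than aPTT, FXI and FXII.** The protocol synopsis and the schedules label the samples that include hsCRP and TNF-alpha as PD cluster B, so a deviation affecting PD evaluation could properly concern those two. This stands in part. Cystatin C and the urine collections have their own rows in the schedule, so the argument is weaker for the renal markers.

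**The count could be made larger.** Adding PT, D-dimers and fibrinogen (3 × 10 = 30) gives 67 exploratory results. Those 30 are coagulation tests from citrate tubes, which a coagulation-related deviation could plausibly affect, so they do not belong in the count.

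**Nothing may happen.** The sets are settled at the blind review and neither document reports an exclusion. This is correct, and it limits the weight of the point.

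**Conclusion.** The point holds as a gap in the reporting populations, not as a protocol violation. As labelled, each dosed participant excluded from the PDS takes up to 37 renal-injury and inflammatory results, 17 of them renal, out of every planned table, graph and listing. That is one sixth of an active dose group or one eighth of pooled placebo. The effect is zero if nobody is excluded.

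The conclusion assumes that the Appendix 4 labels are applied literally. It does not depend on the completion requirement: the deviation criterion alone produces the gap. The completion requirement widens it, and sits awkwardly with protocol 5.2, which says that data gathered before withdrawal enter the statistical analyses.

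The outputs concerned are descriptive, so no formal test result changes. The change is still worth making, because it is nearly free and protects single-participant safety evidence.

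**What to change.** 1. In SAP 16.4, relabel listings 16.2.6.1 and 16.2.6.2 to the Randomised set, with a column flagging PDS membership. This matches the treatment of PK data in SAP 9.2.2.
2. In SAP section 12 and outputs 14.2.3.2.1 and 14.2.3.2.2, summarise cystatin C, KIM-1, NGAL, microalbumin, hsCRP and TNF-alpha on the Safety set. Keep the PDS for aPTT, FXI and FXII.
3. Declare item 2 in SAP section 5 as a change from protocol 10.2.9.2, which names the PDS.

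The cost is SAP wording and a population filter in a few programs. Biomarker and PD tables may then have different n. SAP 7.1 also analyses the Safety set as treated and the PDS as randomised, so a footnote should state the basis of each table. If outputs already exist, listing 16.2.3 (subjects excluded from analysis sets) shows at once whether anyone is affected.
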